6.3.9 Collection of samples for pharmacokinetic assessment

Testing for total serum IgG levels is carried out using the nephelometric method.

Blood samples for the tests will be taken according to a scheme that allows obtaining an adequate pharmacokinetic profile after a single administration of the investigational product for further calculation of pharmacokinetic parameters.

The investigation of PK parameters of the IMP will include at least 20 patients older than 18 years who had been receiving the investigational medicinal product for at least 4 months, and did not have any severe bacterial complications during the study.

PK will be assessed through an additional sampling of 3.5 mL of venous blood (for one sampling) for subsequent determination of patient's levels of immunoglobulin in the samples over 7 days after the infusion of the IMP BP-SCIG 20%. The total volume of venous blood for PK assessment for one patient is 28 mL.

The procedure is performed at Week 21 (Table 4.2.2 – Pharmacokinetic assessment of the IMP). The time of blood sampling is documented.

Structure of PK assessment of the IMP

- 1 PK0 (pre-administration) Before IMP administration (10–30 min prior)
- 2 PK1 (30 minutes) 30 minutes after IMP administration (± 10 min)
- 3 PK2 (3 hours) 3 hours after IMP administration (± 30 min)
- 4 PK3 (1 day) 24 hours after IMP administration (± 5 h)
- 5 PK4 (2 days) 48 hours after IMP administration (± 5 h)
- 6 PK5 (3 days) 72 hours after IMP administration (± 5 h)
- 7 PK6 (4 days) 96 hours after IMP administration (± 5 h)
- 8 PK7 (7 days, threshold level) at 7 days (± 5 h), prior to the next administration of the IMP

The points for pharmacokinetic assessment of BP-SCIG 20% were selected in accordance with the available data on achieving Cmax following subcutaneous administration of the MPs belonging to the subcutaneous immunoglobulin category, and for the purpose of clear demonstration of differences in concentration-time curves for BIOVEN and SCIG.

The investigation of PK parameters of BIOVEN will include subjects aged over 18 years who received treatment with BIOVEN prior to their enrolment in the study and, respectively, throughout the screening period.

PK will be assessed through an additional sampling of 3.5 mL of venous blood (for one sampling) for subsequent determination of patient's levels of immunoglobulin in the samples over 21–28 days after the infusion of BIOVEN. The total volume of venous blood for the PK assessment per one patient is 28–31.5 mL.

The procedures are performed at Visit 3 of the screening period (Table 4.2.3. Pharmacokinetic assessment of IVIG). The time of blood sampling is documented.

Structure of PK assessment of IVIG

- 1 PK0 (pre-administration) Before administration of BIOVEN (10–30 min prior)
- 2 PK1 (15 min) 15 minutes after administration of BIOVEN (± 10 min)
- 3 PK2 (1 hour) 1 hour after administration of BIOVEN (± 15 min)
- 4 PK3 (1 day) 24 hours after administration of BIOVEN (± 5 h)
- 5 PK4 (3 days) 72 hours after administration of BIOVEN (± 5 h)
- 6 PK5 (7 days) 7 days after administration of BIOVEN (± 5 h)
- 7 PK6 (14 days) 14 days after administration of BIOVEN (± 5 h)
- 8 PK7 (21 days) 21 days after administration of BIOVEN (± 5 h)
- 9 PK8 (28 days) 28 days after administration of BIOVEN (± 5 h) (where applicable)

The points for pharmacokinetic assessment of BIOVEN were selected based on previous PK studies of BIOVEN.

The data obtained during the phase of BIOVEN pharmacokinetics will be used to confirm or recalculate the dose adjustment factor for switching from BIOVEN to the IMP.

The procedures of preparation for analysis, collection, storage, transportation of biological material, and completion of accompanying documentation are carried out in accordance with the regulations described in the Laboratory Manual.

Blood collection can be performed, at the study doctor's discretion, in a hospital, on an outpatient basis or by a Sponsor-designated Central Laboratory, in a collection point (if the study subject is mobile in the Investigator's judgement), or by a mobile team.

In the event of deterioration of the patient's well-being or the patient's desire to withdraw from the study, blood sample collection is discontinued. Information about these cases shall be entered in the eCRF, source documentation, and reported to the Sponsor.

In the event a sample was not collected according to the protocol-scheduled time (missed), the information explaining that event shall be entered in the eCRF and source documentation, and sample collection shall be resumed at the next time scheduled according to the Schedule.

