- Assess the frequency of serious adverse reactions;
- Assess the frequency of treatment-emergent adverse events;
- Assess the frequency of treatment-emergent adverse events related to infusion rate;
- Assess the incidence of administration site reactions;
- Assess the frequency of clinically significant deviations in vital signs (blood pressure, body temperature, pulse rate and respiratory rate);
- Assess the frequency of clinically significant deviations in laboratory findings (complete blood count, biochemical findings, markers of intravascular haemolysis, and viral safety parameters);
- Assess the safety data separately in children and adolescents, and compare them with the adult data.

Pharmacokinetic assessment tasks

- to assess the mean threshold concentration of total IgG in plasma before the next administration of the IMP after reaching steady state (after 4 months of treatment) within 6 months (efficacy criterion ≥ 5 g/L);
- to assess the pharmacokinetic parameters of BIOVEN in a subgroup of adult patients with PID who have previously received therapy with BIOVEN in the screening period;
- to assess the pharmacokinetic parameters of the IMP BP-SCIG 20% in a subgroup of 20 adult patients with PID after approximately 4 months of IMP treatment;
- assess the threshold levels of total IgG during the dose titration phase (the dose-effect dependence);
- plot the individual concentration-time curves;
- calculate the following pharmacokinetic parameters:

AUC – area under the curve (AUC $0-t$, AUC $0-\infty$);

T_{max} – the time when maximum concentration of the analyte is reached;

C_{max} – the maximum serum concentration of the analyte;

T_{1/2} – elimination half-life of the analyte;

K_{el} – elimination constant of the analyte;

Cl – serum clearance;

IR – incremental recovery;

Vd – volume of distribution.

Efficacy assessment tasks in the study:

- to evaluate the efficacy of the investigational product in patients with certain humoral and combined primary immunodeficiencies according to the following parameters:
 - the number of cases of serious bacterial infections during the therapy period (**the primary variable**, the criterion of reaching efficacy: less than 1.0 cases of serious bacterial infections per 1 patient over 1 year of therapy);
 - to establish the incidence and the duration of non-serious infectious diseases throughout the course of treatment (a descriptive criterion);

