The assessment of threshold (trough) IgG levels is to be performed in at least 40 patients enrolled in the CT; of these, 20 subjects must be children or adolescents with an appropriate age distribution for this patient group. The trough levels of the IgG from the investigational medicinal product must be assessed after 4 months of treatment with the IMP, prior to the next infusion, once every 4 weeks (once per month/treatment cycle) over 6 months.

The obtained monthly trough IgG levels shall be compared with the trough levels for at least two prior infusions of the previous SCIG or IVIG product. Alternatively, for treatment-naïve patients, a descriptive comparison with published literature (if available) is performed.

Phase of IVIG pharmacokinetic assessment

This phase includes patients older than 18 years who had been receiving previous therapy with the medicinal product BIOVEN prior to their study entry and, accordingly, throughout the screening period.

PK will be assessed through an additional sampling of 3.5 mL of venous blood (per one sampling, a total of 8–9 sampling time points) for subsequent determination of patient's levels of plasma immunoglobulin in the samples over 21–28 days after the infusion of BIOVEN. The total volume of venous blood for the entire IVIG PK assessment per one patient is 28–31.5 mL.

The data obtained during the phase of BIOVEN pharmacokinetics will be used to confirm or recalculate the dose adjustment factor for switching from IVIG to the IMP.

The assessment begins at Visit 3 of the screening period (see Table 4.2.3 Pharmacokinetic assessment of IVIG – BIOVEN). The time of blood sampling is documented.

Phase of IMP BP-SCIG 20% pharmacokinetic assessment

This phase includes at least 20 patients older than 18 years who had been receiving the investigational medicinal product for at least 4 months, and did not have any severe bacterial complications during the trial.

PK will be assessed through an additional sampling of 3.5 mL of venous blood (per one sampling, a total of 8 sampling time points) for subsequent determination of patient's levels of plasma immunoglobulin in the samples over 7 days after the infusion of the IMP BP-SCIG 20%. The total volume of venous blood for PK assessment for one patient is 28 mL.

The assessment is performed at Week 21 (see Table 4.2.2 – Pharmacokinetic assessment of the IMP). The time of blood sampling is documented.

Study phases. Follow-up and completion of the study

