For Cohort C, newly diagnosed (treatment-naïve) patients are required to undergo Visit 1 of the screening period; if meeting inclusion/non-inclusion criteria, the patient proceeds to treatment with the IMP BP-SCIG 20%, starting from Cycle 1.

Table 4.2.2 Schedule of Procedures at Week 21 – Pharmacokinetic assessment of the IMP

Structure of PK assessment*		
No.	PK point	Description
1	PK0 (pre-administration)	Before IMP administration (10–30 min prior)
2	PK1 (30 min)	30 minutes after IMP administration (± 10 min)
3	PK2 (3 hours)	3 hours after IMP administration (± 30 min)
4	PK3 (1 day)	24 hours after IMP administration (± 5 h)
5	PK4 (2 days)	48 hours after IMP administration (± 5 h)
6	PK5 (3 days)	72 hours after IMP administration (± 5 h)
7	PK6 (4 days)	96 hours after IMP administration (± 5 h)
8	PK7 (7 days, threshold)	After 7 days (± 5 h), before the next administration of the IMP

* – The points for pharmacokinetic assessment of BP-SCIG 20% were selected in accordance with the available data on achieving Cmax following subcutaneous administration of the MPs belonging to the subcutaneous immunoglobulin category, and for the purpose of clear demonstration of differences in concentration-time curves for IVIG and SCIG.

Table 4.2.3. Schedule of procedures at Visit 3 – Pharmacokinetic assessment of IVIG

Structure of PK assessment**		
No.	PK point	Description
1	PK0 (pre-administration)	Before administration of BIOVEN (10–30 min prior)
2	PK1 (15 min)	15 minutes after administration of BIOVEN (± 10 min)
3	PK2 (1 hour)	1 hour after administration of BIOVEN (± 15 min)
4	PK3 (1 day)	24 hours after administration of BIOVEN (± 5 h)
5	PK4 (3 days)	72 hours after administration of BIOVEN (± 5 h)
6	PK5 (7 days)	7 days after administration of BIOVEN (± 5 h)
7	PK6 (14 days)	14 days after administration of BIOVEN (± 5 h)
8	PK7 (21 days)	21 days after administration of BIOVEN (± 5 h)
9	PK8 (28 days)	28 days after administration of BIOVEN (± 5 h) (where applicable***)

**The points for pharmacokinetic assessment of BIOVEN were selected based on previous PK studies of BIOVEN.

***Interval between the administrations (every 21–28 days) of BIOVEN, used as a prior therapy, is determined individually for each patient in accordance with the approved instructions for medical use.

4.3. Randomisation and blinding.

No randomisation or blinding is used in this clinical trial.

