6. TREATMENT OF SUBJECTS

6.1. Treatment regimen

The IMP shall be administered subcutaneously.

All patients will receive the investigational medicinal product BP-SCIG 20%, solution for subcutaneous administration manufactured by BIOPHARMA PLASMA LLC.

The IMP BP-SCIG 20% shall be administered at the frequency of once a week for 52 weeks, subcutaneously using a CRONO S-PID4 infusion pump.

The dosing regimen shall be designed to achieve a trough IgG level (at least 5–6 g/L), which will be measured before the next infusion.

Efforts must be taken to maintain serum IgG within the reference range for the corresponding age group of patients.

Individual dose selection and adjustment may be required for each patient, depending on the pharmacokinetic response (IgG level) and clinical response. Threshold levels must be assessed in combination with the incidence of infectious episodes. To reduce the risk of infection, it may be necessary to increase the dose and aim to achieve higher trough IgG levels.

A loading dose of IMP may be required (at the Investigator's decision): at least 0.2–0.5 g/kg (1.0–2.5 mL/kg) of body weight. This dose is distributed across several days, with a maximum daily dose of 0.1 to 0.15 g/kg.

After achieving a steady-state (minimal) level of IgG, maintenance doses are administered at repeated intervals (approximately once a week) to achieve a cumulative monthly dose of 0.4–0.8 g/kg. Each single dose must be administered to different anatomical locations.

Since the bioavailability of SCIGs is 30 % lower than that of IVIGs, partly due to binding to the extracellular matrix and cleavage by tissue enzymes (Wang et al. 2008; Berger et al. 2013), a dose adjustment factor of 1.37 will be used to convert the IVIG dose to the SCIG dose. This is based on historical data for bioequivalence evaluation of these administration routes (Wasserman et al. 2010, 2011; Berger et al. 2011) and meets the requirements of the US Food and Drug Administration (US FDA), according to which the SCIG doses must be adjusted to ensure an equivalent AUC for total IgG compared to previous IVIG therapy. Dose calculation for patients who received IVIG prior to the start of their participation in the study (John W Sleasman et al. 2019):

The initial dose of SCIG

$$\text{IgG} = \frac{\text{Previous IVIG dose (in grams)} \times 1.37}{\text{Number of weeks between IVIG administrations}}$$

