For the variables measured according to the schedule of patient assessments more often than twice, evaluate the changes in quantitative variables over time using a one-way analysis of variance (ANOVA) or rank analysis depending on the normality of the distribution, checked using the Shapiro–Wilk test. In this setting, the dependent variable is the parameter being analysed, and the “visit” factor is the fixed parameter. Evaluate the value and significance for the reliability of the difference between the visits using post hoc analysis with Tukey's test (for ANOVA) or the Wilcoxon signed rank test with Holm's adjustment (for the rank test). To verify the preconditions for the use of analysis of variance, the normal distribution of residuals will be tested using the Shapiro–Wilk test. If the residuals are not distributed normally, a corresponding rank analysis will be performed. Assessment of pharmacokinetic parameters will be informed by fundamental principles of descriptive statistics for the main pharmacokinetic parameters, preliminary assessment of statistical homogeneity of study patient population, as well as by the obtained values for the parameters and the homogeneity of their distribution.

For each patient, individual pharmacokinetic parameters will be calculated:

Cmax, the maximum serum concentration of the analyte;

AUC0-t, the area under the concentration-time PK curve (from zero to last blood sampling, where the concentration of the analyte is higher than or equal to the lower limit of quantification [LLOQ]);

AUC0-∞, the area under the concentration-time PK curve (from zero to infinity).

Tmax, the time to maximum concentration of the analyte;

t1/2, the elimination half-life of the analyte;

Kel, the elimination rate constant of the analyte;

IR, the incremental recovery of class G immunoglobulin;

Vd, volume of distribution;

Cl, serum clearance;

$((AUC_{0-\infty} - AUC_{0-t})/AUC_{0-\infty})$, the residual (extrapolated) area (AUCextrapol).

The values of Cmax and Tmax were calculated using a model-independent method, as the largest of the measured concentrations in each patient and as a corresponding time of observed maximum, respectively.

AUC0-t was calculated using trapezoidal method.

All other parameters were calculated using a model-independent method.

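### AUC0-∞ and its extrapolated share cannot be taken from a 7-day steady-state profile, and half-life, Kel and Vd from the same profile are unreliable

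*Protocol*

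**What the plan says.** **Timing.** The product is "administered at the frequency of once a week for 52 weeks" (6.1). On the profile, 4.2 states: "The assessment is performed at Week 21". Only adults "who had been receiving the investigational medicinal product for at least 4 months" are eligible (6.3.9). Section 3 places trough sampling "after reaching steady state (after 4 months of treatment"), so the protocol regards the profile as a steady-state one.

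**Samples.** Table 4.2.2 has eight points: pre-dose, 30 minutes, 3 hours, and days 1, 2, 3, 4 and 7. The last is taken "before the next administration of the IMP". No sample follows drug withdrawal by more than a week, because Visit 17, one week after the final dose, ends the study (4.2).

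**Description.** Section 6.3.9 nevertheless calls this "a scheme that allows obtaining an adequate pharmacokinetic profile after a single administration of the investigational product".

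**Parameters.** Section 9.7 lists, for each patient, "AUC0-∞, the area under the concentration-time PK curve (from zero to infinity"), the extrapolated area as a share of it, half-life, Kel, clearance, Vd and incremental recovery (IR). Section 3 asks for AUC0-∞ and the extrapolated area as well. Section 4.1 makes half-life, elimination constant, clearance, Vd and IR secondary PK endpoints. Apart from the trapezoidal rule for AUC0-t, 9.7 gives no formula and says only that the other parameters are model-independent.

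**Main comparison.** Section 9.6 names steady-state AUC-t against BIOVEN and trough IgG as the main PK parameters.

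**The concern.** AUC0-∞ and its extrapolated share describe the complete response to one dose. At Week 21 the serum IgG is the sum of what remains from all earlier weekly doses, so extrapolating the curve to infinity adds their tails to the area. The terminal slope that this needs must come from the few days after the peak, when IgG has hardly fallen and absorption may still be running.

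At stake are several named secondary PK endpoints, the between-cohort comparison and the comparison with published values in section 3. These would carry numbers that are wrong by a known multiple (AUC0-∞ and anything built on it) or too imprecise to interpret (half-life, Kel, Vd).

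**Working it through.** The protocol states no half-life, extrapolated share or clearance, so there is no figure of its own to reproduce.

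**Inputs from the protocol.** Dosing interval τ = 7 days; sampling times as in Table 4.2.2; BIOVEN interval 21–28 days (Table 4.2.3).

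**Assumptions (not in the protocol).** One compartment, linear kinetics, first-order absorption; IgG half-life 14–40 days; absorption half-life 0.7–2 days; assay CV 3–5%; no endogenous IgG unless stated. As a cross-check, steady state after 4 months (about 120 days), read as 4–5 half-lives, implies 120/5 = 24 to 120/4 = 30 days.

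**1. Carry-over.** At steady state, interval AUC = F × dose/Cl, which is also the single-dose AUC0-∞. The extrapolation adds C(7)/k. In units of F × dose/V, interval AUC = 1/k, so

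AUC0-∞ / interval AUC = 1 + C(7), with C(7) = ka/(ka − k) × [e^(−7k)/(1 − e^(−7k)) − e^(−7ka)/(1 − e^(−7ka))].

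For half-life 30 days and absorption half-life 1 day: k = 0.0231, ka = 0.693, C(7) = 1.034 × (5.696 − 0.008) = 5.88. The ratio is 6.88 (6.89 by trapezoid on the protocol's times) and the extrapolated share is 5.88/6.88 = 85%.

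| Half-life (days) | AUC0-∞ / interval AUC, true k | Extrapolated share |
|---|---|---|
| 14 | 3.5–3.7 | 72–73% |
| 24 | 5.6–5.8 | 82–83% |
| 30 | 6.8–7.0 | 85–86% |
| 40 | 8.9–9.1 | 89% |

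With k fitted to days 3, 4 and 7 (no noise), the ratio is 3.8–16.7 over the same range.

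**2. Clearance and Vd, if based on AUC0-∞.** With the fitted slope and half-life 24–30 days, dose/AUC0-∞ is 0.08–0.17 of the true clearance and Cl/Kel is 0.15–0.19 of the true Vd. If clearance is instead dose/interval AUC, it is recovered correctly as Cl/F. Vd from that clearance is still 1.1–2.0 times too high, because Kel is too small.

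**3. Terminal slope.** From day 3 to day 7 elimination alone lowers IgG by 1 − e^(−4k): 18% at 14 days, 11% at 24, 9% at 30, 7% at 40. Continuing absorption makes the observed fall smaller. The noise-free fitted half-life is 1.1–2.0 times the truth (up to about 2.4 times with 20% endogenous IgG).

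For a log-linear fit on days 3, 4 and 7, Σ(t − t̄)² = 8.67, so SD(slope) = CV/√8.67 = 0.0102 at 3% CV and 0.0170 at 5%. For half-life 30 days and absorption half-life 1 day the noise-free slope is 0.0188 (apparent half-life 37 days). The chance of a zero or positive trend is Φ(−0.0188/0.0102) = 3% at 3% CV and Φ(−0.0188/0.0170) = 13% at 5% CV. For half-lives of 24–30 days and all the absorption rates, this share is 0.4–12% at 3% CV and 6–24% at 5% CV. Those patients have no half-life, Kel or AUC0-∞. Among the others, for a true 30 days at 5% CV (absorption half-life 1 day), the 10th–90th percentile of the estimates is about 17–125 days.

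**4. BIOVEN, if the same extrapolation were used.** The ratio is 1/(1 − e^(−kτ)). For τ = 21 days it is 2.00, 2.60 and 3.28 at half-lives of 21, 30 and 40 days; for τ = 28 days it is 1.66, 2.10 and 2.60.

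**The case against.** Much of the case on the other side stands.

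- **The main PK results are untouched.** The primary PK endpoint is the trough (4.1), and 9.6 compares steady-state AUC-t, on which the dose-factor objective rests. None of these needs extrapolation. A reader might infer that primary objective 1 or the dose factor is compromised; the protocol does not support that.
- **No clearance formula is given.** A reader might infer that clearance will certainly be several-fold too low. Dose over interval AUC is also model-independent and would be sound, and formulas are commonly left to the SAP. The clearance error is therefore conditional.
- **BIOVEN.** A reader might infer a built-in false difference between products. Sections 3 and 9.7 tie the full parameter list to the 20 adults on the investigational product, and no text explicitly requires AUC0-∞ or clearance for BIOVEN.
- **The phrase itself.** The words about a single administration may only mean one infusion, since the next paragraph of 6.3.9 requires 4 months of prior treatment.
- **Half-life and IR.** Half-life bias is about 1.1–2-fold, so it is not several-fold wrong. IR can be taken as the rise above the pre-dose sample; it is imprecise, not invalid.

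What does not fall away is that AUC0-∞ and its extrapolated share are affirmatively required from a 7-day steady-state interval. No choice of formula makes the terminal slope reliable with these samples.

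**Conclusion.** The point holds for the secondary PK parameters of the investigational product and should be fixed; it is not a threat to the trial's main PK conclusions.

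AUC0-∞ is wrong as specified, by about 3.5–9 times even with the true elimination rate, for any half-life from 14 to 40 days. That multiple depends on the assumed half-life and linear kinetics, but it stays several-fold throughout the range. Clearance and Vd share the error only if computed from AUC0-∞. Half-life and Kel are moderately biased and very imprecise, and for half-lives of 24–30 days roughly 1–24% of patients would have none; these shares also rest on the assumed absorption rate and the 3–5% assay CV.

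If AUC0-∞ were also computed for BIOVEN, its inflation would be about 1.7–3.3-fold (half-life 21–40 days). AUC0-∞, or clearance derived from it, must therefore not be compared between the products.

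**What to change.** - **6.3.9:** replace the wording about a single administration with *over one dosing interval at steady state*.
- **Sections 3 and 9.7:** replace AUC0-∞ and the extrapolated area with AUC over the dosing interval (0–7 days for the investigational product; the actual 21- or 28-day interval for BIOVEN) and average concentration.
- **Clearance:** define it as dose per interval divided by interval AUC, labelled apparent (Cl/F) for the investigational product. Note that endogenous IgG is included in the measured level.
- **IR:** define it as the rise over the pre-dose sample (PK0) and report it descriptively.
- **Half-life, Kel and Vd for the investigational product:** keep them only as descriptive apparent values, with a rule stated in advance (reported only where concentration declines over the terminal points, with the number of patients not estimable). Leave them out of the cohort and literature comparisons.
- **BIOVEN half-life:** take an apparent value from the decline between day 7 and the end of the interval.

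Deleting all the named secondary endpoints is not necessary.

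**Cost.** No new samples or visits. It needs a protocol amendment, which 11.2 may class as substantial because it touches statistical methods, and it leaves fewer parameters to set beside published tables. It is best done before the PK data are analysed, so that the change cannot look selective.
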